We have developed a simple, comfortable, and straightforward silicone-injected, bidirectional oxygenation mouthpiece that effectively delivers PEEP with every breath (image 1). The purpose of this pilot study is to demonstrate the safety and feasibility of the bidirectional oxygenation mouthpiece in cardiac surgical patients, compare this novel device to conventional incentive spirometry, and identify any potential benefits to respiratory dynamics.

Image 1. Bidirectional oxygenation mouthpiece

1a – PEEP Mouthpiece valve closed during expiration.

1b – PEEP Mouthpiece valve open during inhalation.

Initial testing using the bidirectional oxygenation mouthpiece on healthy subjects has been encouraging. Crouse et al. studied nine subjects during exercise and reported that the “Wearable Positive End-Expiratory Pressure Valve Increases Aerobic Capacity and Performance.”²⁵ Subjects were assigned at random to the novel bidirectional oxygenation mouthpiece, a standard oxygenation mouthpiece, or nothing at all. Subjects wearing the bidirectional oxygenation mouthpiece showed an improvement in VO₂ max of 6.1% compared to the standard mouthpiece and 4.0% compared to no mouthpiece. The endurance test showed an improvement of 6.5% compared to the standard mouthpiece and 6.0% compared to no mouthpiece. All results had p-values < 0.05. No adverse events were reported during the testing. Furthermore, the consumer version of this device, which is being used by athletes during vigorous exercise, has sold over 2000 units to date with no reported adverse events.

Research Design and Methods

Design

This pilot study will utilize a single center, prospective, randomized controlled study design.

Target Study Population

Patients undergoing coronary bypass and/or valve replacement will be evaluated for study eligibility, and will be preoperatively selected according to the below criteria:

Inclusion Criteria

1. Undergoing CABG and/or valve replacement surgery
2. Able to provide written informed consent
3. Maintenance of an arterial line postoperatively

Exclusion Criteria

1. Active smoking, within three months of surgery
2. FEV1 <75% predicted
3. Relative risk to develop pulmonary barotrauma as evident by history of pneumothorax or emphysema
4. Unable or unwilling to provide informed consent, cognitive impairment

Study Endpoints

Primary Endpoint

1. PaO₂ level at 1, 6, 12 and 24 hours post-extubation.

Secondary Endpoints

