1. Atelectasis on CXR (Atelectasis Severity Score) immediately post-op and on postoperative days 1-4
2. Oxygen requirement 1, 6, 12 and 24 hours post-extubation and daily each morning
3. CO₂ level at 1, 6, 12 and 24 hours post-extubation
4. FEV1 and FVC measurements pre-op and on postoperative day 3
5. Respiratory rate 1, 6, 12 and 24 hours post-extubation then daily each morning
6. Peak body temperature every 24 hours (as a marker of atelectasis)

Study Procedures

After an eligible patient has provided written informed consent, he/she will be randomly assigned to one of two study cohorts: incentive spirometer (Control Arm) or Bidirectional Oxygenation Valve (G02 Mouthpiece).

Permuted block randomization will be employed to ensure balance between groups when the number of recruited patients reaches a multiple of the block size. All patients will undergo additional postoperative respiratory therapy, including: deep breathing exercises, directed cough, early mobilization and optimal analgesia per routine care. Mouthpieces for each study arm will be provided to a patient throughout the hospitalization.

Both cohorts will use the assigned device following similar protocols:

1. Proper positioning of the patient in bed.
2. Proper positioning of the incentive spirometer or Go2 mouthpiece.
3. A breath cycle will consist of 10 breaths every hour while awake. See instructions in Appendix A.
4. The research assistant will provide adequate training for both devices and will supervise their use.

Arterial blood gases (ABGs) will be collected on 2L/NC (x 5 min) at 1, 6, 12 and 24 post-extubation (+/- 1 hour). Pt. will be asked to use assigned device (incentive spirometer or GO2 mouthpiece) before each ABG is collected. Blood samples will be tested locally at the Emory St. Joseph's Hospital Laboratory.

A chest radiograph will be obtained immediately post-op and daily on post-op days 1-4 to assess the presence of atelectasis using the atelectasis severity score. X-rays will be read by a single radiologist in a blinded fashion.

Respiratory rate will be measured 1, 6, 12 and 24 hours post-extubation then daily each morning.

Body temperature will be measured per nursing routine (as a marker of atelectasis). Temperature max will be recorded each 24 hours.

Schedule of Assessments

Study Procedures	Baseline (up to 30 days before surgery)	Post-Op	POD 1	POD2	POD3	POD4
Consent	X					
Pulmonary function test (PFT)	X				X ²	
Randomization	X					

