Treatment: breathing exercises with mouthpieces		X	X	X	X	X
Arterial blood gas (ABGs)			X ¹	X ¹		
Chest x-ray with Atelectasis Severity Score	X	X	X	X	X	X
RR and body temp		X	X	X	X	X
Peak Body Temp			X	X	X	X
Adverse Events		X	X	X	X	X
Use of Device Questionnaire						X ³

¹ABGs 1, 6, 12 and 24 post extubation.

²Performed for research purposes only

³Can be done from POD4 up until discharge from hospital

Statistical Analysis Plan

As a pilot study, our goal is to examine the feasibility and safety of conducting this pilot study on a larger scale. We evaluate the feasibility of recruitment, retention, assessment and implementation of the proposed interventions. We wish to identify any potential flaws in the study design and potential challenges in the subsequent large-scale study. Moreover, the pilot data will give us a first impression of the variability and effect sizes of PaO₂ in the patient population of interest and thus assist in the sample

size and power calculation of the subsequent larger study. Finally, the data that we collect from this pilot will help identify modifications needed in the planning and design of the subsequent study.

We will also assess safety of the new mouthpiece with close monitoring of patient symptoms, physical exam, PaO₂, PCO₂, CXR results, vital signs, and temperature. At the conclusion of the study, we will attempt to assess between-group differences, but given that low power is characteristic of pilot studies, statistical significance is not the focus of the analysis. However, we plan to provide statistical summaries that would be useful in the subsequent study and to other researchers, such as number of patients screened per month, number of patients enrolled per month, proportion of screen eligible who enrolled, lost-to-follow rate, study costs.

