We will also summarize patient characteristics at baseline and during follow-up using mean ± standard deviation (or median and interquartile range, as appropriate) for quantitative variables and frequency (percentage) for categorical variables. Summary statistics on PaO₂ will be reported at each measurement occasion for each group. We will also attempt to fit a mixed effects model to examine between-group differences in PaO₂ at each study visit. An error covariance structure most appropriate to the data will be chosen. Every effort will be made to ensure complete follow-up, and to handle missed visits, missingness at random will be assumed. Finally, a qualitative review will also be provided, and this will include, among others, an evaluation of the representativeness of the patient volunteers, a discussion on how to refine the data collection tools, how to improve the database, how to track patients better as well how to improve implementation of the proposed intervention.

Sample Size and Accrual

The sample size for this pilot study will include 20 patients undergoing coronary bypass and/or valve replacement surgery, however, we anticipate that approximately 40 patients may be consented to account for patients that may be ineligible, screen fail, or withdraw from study. This is the number of anticipated eligible patients that may be recruited over a period of 2 months. This number is deemed sufficient to demonstrate the feasibility and safety of the bidirectional oxygenation mouthpiece.

General Design Limitations

Possible pitfalls may include unsupervised use of the assigned mouthpiece or unexpected non-pulmonary complications secondary to the surgery which may affect the results of the analysis. Also, subjects opting out of the study may represent a potential drawback, secondary to pain or fatigue, or evidence of hyperventilation and/or respiratory alkalosis.

Protection of Human Subjects

Institutional Review Board (IRB) Review and Informed Consent

Screening and enrollment will not begin until the Emory University IRB has approved the study protocol and informed consent form.

A physician investigator or study team designee(s) will obtain the informed consent document and verify the date of consent document is within the IRB approval period.

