Subject confidentiality will be guaranteed by storing all data collected in a password-protected database with no associated PHI or patient identifier information included. Patients in this database will only be identified via a unique study ID number. This study ID number will link the electronic data set of each patient to their PHI that will be stored separately in the research study binder.

Subject Safety

Subject safety is of utmost importance throughout this study. The use of oxygenation devices such as the incentive spirometer has not been associated with pulmonary complications or other adverse events. Nonetheless, patients with history of chronic obstructive pulmonary disease or those at risk of developing barotrauma will be excluded from this study.

Adverse Events

Patients will be assessed for the following adverse events:

1. Hypoxia (O₂ saturation <85%)
2. CO rise 20% over baseline
3. Increasing O₂ requirement (non-rebreather mask, biflow, BIPAP requirement)
4. Reintubation

5. Pneumothorax

All serious adverse events will be assessed and reported per the Emory IRB Policies and Procedures.

Data Collection and Monitoring

Study data will be collected from the patient's electronic medical records and from the local Society of Thoracic Surgeons (STS) clinical outcomes database. All information will be entered in a de-identified fashion into a password protected Microsoft Excel spreadsheet created for the study. All study data will be coded using indirect identifiers consisting of a unique numeric study ID code linked to each study participant's name to enable verification of study data against source data, as needed.

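### The sample of 20 is called sufficient to demonstrate safety on a recruitment basis alone; with about 10 device patients (1:1 assumed), an event never seen could still have a rate up to 30.8% (exact two-sided 95% limit)

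*Combined protocol and SAP*

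**What the plan says.** All references are to the combined protocol and SAP.

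- **Sample Size and Accrual** sets the sample at 20 and adds that "we anticipate that approximately 40 patients may be consented", to allow for ineligibility, screen failure and withdrawal. The basis follows: "This is the number of anticipated eligible patients that may be recruited over a period of 2 months". Then comes the conclusion: "This number is deemed sufficient to demonstrate the feasibility and safety of the bidirectional oxygenation mouthpiece".
- **Background and Significance**, in the paragraph introducing the device, states the aim: "The purpose of this pilot study is to demonstrate the safety and feasibility of the bidirectional oxygenation mouthpiece in cardiac surgical patients". This is a purpose; sufficiency is claimed only in Sample Size and Accrual.
- **Study Procedures** describes two cohorts and says "Permuted block randomization will be employed to ensure balance between groups". It gives no ratio.
- **Statistical Analysis Plan** says "We will also assess safety of the new mouthpiece with close monitoring of patient symptoms, physical exam", followed by blood gases, chest X-ray, vital signs and temperature. No threshold or interval is attached to any of them. On between-group differences it says that "given that low power is characteristic of pilot studies, statistical significance is not the focus of the analysis".
- **Adverse Events** opens with "Patients will be assessed for the following adverse events" and lists five events, with no expected or acceptable rate for any.

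**The concern.** A statement that a sample is sufficient to demonstrate safety needs something to be sufficient for: an event rate to exclude, or a precision to reach. The plan gives neither. The number comes from recruitment, and a recruitment forecast says nothing about what the data can rule out.

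Safety appears in the objective, in the stated purpose and in the sample size rationale. Under the present wording, a pilot in which a listed event did not occur could be described as having met its purpose, with nothing beside the result to show how wide the uncertainty is. The earlier experience that the protocol reports, nine exercising subjects and consumer sales to athletes, does not come from cardiac surgical patients and so does not fill the gap.

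**Working it through.** **The plan's own figure.** The 20 cannot be reproduced by calculation. No significance level, power, effect, event rate, margin or interval width is given.

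**Inputs**

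- Total sample: 20 (Sample Size and Accrual).
- Arms: 2 (Study Procedures).
- Device patients: 20/2 = 10, assuming 1:1. The ratio is not stated, so 8 to 12 is also shown.
- Most favourable reading: all of about 40 consented patients are randomised 1:1, giving 40/2 = 20 device patients.
- Confidence level: 95%, assumed. The plan states none.

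**Upper limit when a given event is seen in 0 of n device patients (Clopper-Pearson)**

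Two-sided 95%: 1 − 0.025^(1/n). One-sided 95%: 1 − 0.05^(1/n).

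| Device patients n | Two-sided 95% | One-sided 95% |
|---|---|---|
| 8 | 36.9% | 31.2% |
| 10 | 1 − 0.025^(1/10) = 30.8% | 1 − 0.05^(1/10) = 25.9% |
| 12 | 26.5% | 22.1% |
| 20 | 1 − 0.025^(1/20) = 16.8% | 13.9% |

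With one event in 10, the exact two-sided 95% interval is 0.3% to 44.5%.

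**How often 10 device patients would show none of a given event: (1 − p)^10**

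- p = 2%: 0.98^10 = 0.817
- p = 5%: 0.95^10 = 0.599
- p = 10%: 0.90^10 = 0.349

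The 2% and 5% come from Background and Significance, which cites that range for pneumonia, unplanned reintubation and prolonged ventilation. Of these, only reintubation is on the Adverse Events list. The range is a background rate for a group of complications, used here for scale; it is not a rate of harm from the device. The 10% is an assumed value.

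**Device patients needed, with zero events, to exclude a rate p**

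Smallest n with (1 − p)^n ≤ 0.05 (one-sided) or ≤ 0.025 (two-sided):

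- p = 10%: 29 or 36
- p = 5%: 59 or 72

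These counts give scale only. They are not a proposed sample size.

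**Can the listed events be counted?** The second listed event is a 20% rise in CO from baseline. CO is not defined there. The Schedule of Assessments places blood gases on POD 1 and POD 2 only, timed from 1 hour after extubation, with none in the baseline column. As written, that count may not be computable.

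**The case against.** The strongest reply is that this is a pilot and says so. The Statistical Analysis Plan aims to examine feasibility and safety for a larger study, plans monitoring instead of a safety test, and disclaims statistical significance. No analysis step would declare safety shown, so the fault is one of wording.

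Part of this stands. There is no safety test for a small sample to invalidate, and 20 patients can serve feasibility and a first estimate of PaO₂ variability. But the low-power caveat is tied to between-group differences, and nothing in it limits the later, unqualified sentence under Sample Size and Accrual. Pilot status makes a claim to demonstrate safety harder to support.

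A second reply is that counts will be reported anyway, so a reader could work out the limit. The plan does provide frequencies and percentages for categorical variables, but under patient characteristics. It names neither adverse events by arm nor intervals.

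A third is that 10 is uncertain. The sentence on recruitment follows the clause about 40 consented patients, and withdrawals are counted within the 40, so more than 10 patients could use the device. That is fair, and the 20-patient row covers it.

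A reader might infer more than the documents support:

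- **That the device is unsafe, or that the 2–5% range is its harm rate.** The upper limit describes ignorance, and the range is a background rate for a group of complications.
- **That the trial must be enlarged.** The plan's pilot aims do not require it.
- **That Background and Significance also claims sufficiency.** It states only a purpose.

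**Conclusion.** The point holds as a fault in what the plan says its sample can show. If a given event is not seen in about 10 device patients, rates up to 30.8% remain compatible with the data (exact two-sided 95%). The conclusion does not hinge on the assumptions: the limit is 25.9% one-sided, 36.9% to 26.5% for 8 to 12 device patients, and 16.8% for 20. The 30.8% rests on 1:1 allocation, a 95% level, and a count of patients with the event.

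The sample can reveal frequent harms and support feasibility. It cannot demonstrate safety. The sentence should be changed, but it does not invalidate the trial.

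**What to change.** 1. **Sample Size and Accrual.** Replace the sufficiency sentence with: *The sample size of 20 is based on expected recruitment and serves to assess feasibility and to estimate the variability of PaO₂. Safety is descriptive: if allocation is 1:1 (about 10 device patients) and a given event does not occur, the exact two-sided 95% upper limit for its rate is about 31%.* State the actual allocation ratio, and adjust the figure if it is not 1:1.
2. **Background and Significance, and Study Objective.** Reword the purpose so that the pilot is to assess feasibility and describe safety. Bring the objective, which now sets out to determine both, into line.
3. **Statistical Analysis Plan.** Add that each event listed under Adverse Events will be reported by arm, as patients with the event over patients treated in that arm, with exact two-sided 95% confidence intervals.
4. **Adverse Events and Schedule of Assessments.** Before the CO event is counted, reconcile what CO and baseline mean, since the schedule shows no baseline blood gas.

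The cost is a few wording changes, one reporting line, one definition to reconcile, and a less favourable safety statement. Sample size, endpoints and the PaO₂ analysis are unchanged.

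### The adverse event list has five items and no catch-all category: other non-serious events have no stated route into the safety results, recording starts only after surgery, and no relatedness assessment or by-arm summary is specified

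*Combined protocol and SAP*

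**What the plan says.** Safety is half of the Study Objective, and Sample Size and Accrual asserts that 20 patients are enough to show it. Data Management adds that no data safety monitoring plan is needed. The safety answer therefore rests on what is recorded as an adverse event.

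- **Adverse Events:** "Patients will be assessed for the following adverse events", followed by hypoxia, "CO rise 20% over baseline", a rising oxygen or ventilatory support requirement, reintubation and pneumothorax. There is no further category. The next sentence reads: "All serious adverse events will be assessed and reported per the Emory IRB Policies and Procedures".
- **Statistical Analysis Plan:** "We will also assess safety of the new mouthpiece with close monitoring of patient symptoms, physical exam", and then blood gases, chest radiograph results, vital signs and temperature. No adverse event table, by arm or otherwise, is described.
- **General Design Limitations:** the protocol expects "unexpected non-pulmonary complications secondary to the surgery which may affect the results of the analysis". It also expects some patients to opt out because of pain, fatigue, hyperventilation or respiratory alkalosis.
- **Schedule of Assessments:** the adverse event row is marked from Post-Op to POD4 and is blank at baseline ("Adverse Events X X X X X").
- **Appendix A:** patients in both arms are told to practise with their device several times a day before surgery.

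**The concern.** The SAP describes safety broadly, while the Adverse Events section gives a short list as what patients are assessed for. A non-serious event outside that list, such as mouth discomfort, dizziness or pain on forced exhalation, has no adverse event category. If the plan is followed as written, a patient who stops the device for one of the reasons the protocol foresees could appear only as a withdrawal, with no adverse event. For a first comparison of a new device in cardiac surgical patients, tolerability is a large part of what a pilot should pass on to the larger study.

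The second gap is in how listed events are interpreted. Reintubation after cardiac surgery can have a surgical or a respiratory reason. With no record of cause and no planned summary by arm, the reader of the results cannot tell the two apart.

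**Working it through.** **Scope: what is promised or foreseen, against what the list can hold**

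| Source | Item | Listed event it corresponds to |
|---|---|---|
| SAP | PaO₂ | Hypoxia (defined by saturation) |
| SAP | PCO₂ | Second item, if CO is a misprint for CO₂ |
| SAP | Chest radiograph | Pneumothorax |
| SAP | Symptoms, physical examination | None; no row in the Schedule |
| SAP | Vital signs, temperature | None; the Schedule shows respiratory rate and temperature only |
| General Design Limitations | Pain, fatigue | None |
| General Design Limitations | Hyperventilation, respiratory alkalosis | None; the second item is a rise, and these involve a fall in CO₂ |
| General Design Limitations | Non-pulmonary surgical complications | None; only the serious-event sentence applies |

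Three of the SAP's safety measures match the list. Symptoms and examination do not, nor do any of the four foreseen reasons for opting out.

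**Timing.** Device use can begin before surgery (Appendix A), and the baseline window runs up to 30 days before it. The first adverse event mark is Post-Op. Anything in between has no scheduled recording.

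**Sample size.** The figure of 20 cannot be reproduced as a safety calculation. No event rate, threshold or precision target is given, and the number is tied to expected recruitment over two months.

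**How far the control arm can absorb background reintubations**

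Inputs: 20 patients (Sample Size and Accrual); 10 per arm, an assumption because the allocation ratio is not stated; and a reintubation risk *p* of 2–5%, equal in both arms. The 2–5% comes from Background and Significance, which applies it to pneumonia, unplanned reintubation and prolonged ventilation without saying whether it is per event or combined. Using it for reintubation alone, whatever the cause, is an assumption. If the figure is combined, the risk is lower.

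- At least one event in the device arm, 1 − (1 − *p*)^10: at 2%, 1 − 0.98^10 = 18.3%; at 5%, 1 − 0.95^10 = 40.1%.
- At least one event among all 20, 1 − (1 − *p*)^20: 33.2% and 64.2%.
- More events in the device arm than in control by chance, (1 − P(tie))/2 for two binomial counts with n = 10: at 2%, (1 − 0.6956)/2 = 15.2%; at 5%, (1 − 0.4635)/2 = 26.8%.
- One event in an arm of 10 is a crude rate of 1/10 = 10%.

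Background events in the device arm are therefore quite likely, and a chance imbalance is not rare.

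**The case against.** The case on the other side has real force.

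- A reader might infer that non-respiratory harm goes uncounted. The documents do not support that. The sentence after the list covers all serious adverse events, without limiting them to the five items. The gap concerns non-serious events, and the lack of a stated route from IRB reporting into the trial's own results. The IRB policy may require a judgement of cause for serious events; it is not in the documents, so this cannot be settled.
- A reader might infer that surgical reintubations are counted as device harm. No text attributes any listed event to the device. Events are assessed in both randomised arms, and randomisation is the design's answer to background events. That answer is sound on average but weak at about 10 per arm.
- A reader might infer that one misclassified event would overturn the safety conclusion. There is no safety threshold or test for it to overturn, and the SAP says that significance is not its focus.
- The text never says that only the five items count. Other sources exist: medical records, the surgical outcomes database and the device questionnaire from POD4. They may hold tolerance data, but the questionnaire's content is not described and nothing links any of these sources to adverse events.
- Cause would be judged by investigators. The only blinding stated is of the radiologist, so a cause column could itself introduce bias. This stands, and it limits how the column should be used.

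**Conclusion.** The point holds in this limited form and should be acted on. As written, the plan would give an incomplete safety result: non-serious events outside five items have no stated place in it, including four that the protocol foresees; pre-operative device use falls outside the recording window; and neither relatedness nor a by-arm adverse event summary is specified. A reintubation for a surgical reason would be recorded in the same way as one for respiratory failure, in whichever arm it occurs.

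The number of non-serious events that would be missed cannot be given, because the documents contain no rate for them. The only size that can be shown is for background reintubation: an 18–40% chance of at least one in the device arm, and a 15–27% chance of an unfavourable imbalance with no true difference. Both rest on 1:1 allocation and on using the 2–5% incidence for reintubation alone. Describing the list as respiratory also assumes that the second item means CO₂, which the protocol should state.

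**What to change.** Keep the five items as events of special interest and replace the opening sentence of Adverse Events with wording such as: *All adverse events, serious and non-serious, will be recorded from first device use to the end of follow-up, including the five below, each with onset time, seriousness, whether it led to stopping the device, and the investigator's view of cause (device, surgery, other).* Extend the Schedule row to match, and say when follow-up ends.

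Add to the SAP a table by randomised arm of the number of patients with any event, with each listed event, and with an event leading to stopping the device, all regardless of cause. Show device-related events and reintubation by cause as a supplement, with a note that cause was judged without stated blinding. The all-cause comparison should stay primary, because randomisation protects it and the cause judgement is not protected in the same way.

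The cost is one more case-report page, more background surgical events in the tables, and some collection before admission for patients who practise at home. For about 20 treated patients this is modest, and it alters what is recorded, not how patients are managed.

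### Adverse event 2 is a 20% rise over a baseline for which no blood gas is scheduled, so its count depends on the gas picked; separately, the pre-op FEV1/FVC has no stated use in the POD3 comparison (minor)

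*Combined protocol and SAP*

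**What the plan says.** **Event 2.** Item 2 of the Adverse Events list reads "CO rise 20% over baseline". The protocol does not say which measurement is the baseline. CO₂ is also a secondary endpoint, "CO₂ level at 1, 6, 12 and 24 hours post-extubation", and PCO₂ is among the safety measures named in the Statistical Analysis Plan section.

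**When gases are drawn.** Study Procedures sets four gases, at 1, 6, 12 and 24 hours after extubation, each on 2 L nasal cannula oxygen. It adds: "Pt. will be asked to use assigned device (incentive spirometer or GO2 mouthpiece) before each ABG is collected". In the Schedule of Assessments, the row "Treatment: breathing exercises with mouthpieces" is marked from Post-Op onward. The arterial gas row is marked under POD1 and POD2 only. The column headed Baseline covers up to 30 days before surgery and carries no gas.

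**Spirometry.** Secondary endpoint 4 is "FEV1 and FVC measurements pre-op and on postoperative day 3". The Statistical Analysis Plan section specifies a mixed model for PaO₂. For other variables it promises descriptive summaries at baseline and during follow-up.

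**The concern.** Safety is part of the study objective, and the sample size section calls 20 patients enough to demonstrate it. One of the five named events needs a reference value that the planned data do not contain under the protocol's own meaning of Baseline. Someone abstracting the data could use the 1 h gas, the preceding gas or an unscheduled gas from the chart without contradicting the text. Two people could then report different counts from the same patients. With 20 patients, reclassifying one moves the event rate by 1/20 = 5 percentage points.

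The spirometry point is separate and smaller. A pre-op value is collected for every patient, yet no between-group comparison that uses it is stated.

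**Working it through.** The plan gives no expected event rate, CO₂ mean or SD, so it has no figure to reproduce. All CO₂ values and correlations below are assumptions.

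**1. Candidate references for event 2**

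| Candidate | Scheduled? | Condition |
|---|---|---|
| Baseline visit | No gas marked | – |
| Post-Op column | No gas marked | – |
| 1 h gas | Yes | Nasal cannula, after requested device use |
| Preceding gas | Yes, for the 6, 12 and 24 h gases | Nasal cannula, after requested device use |
| Unscheduled chart gas | Not in the plan | Unknown; may be ventilated |

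Taking the 1 h gas as reference also leaves three gases, not four, to be compared with it.

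**2. One assumed patient.** PaCO₂ is 37 mmHg pre-op, then 45, 43, 41 and 40 at 1, 6, 12 and 24 h.

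- Pre-op reference: 45/37 − 1 = +21.6%, an event.
- 1 h reference: 43/45 − 1 = −4.4%, 41/45 − 1 = −8.9%, 40/45 − 1 = −11.1%, no event.

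**3. Translating one reference into another.** If the 1 h gas differs from an earlier gas by a fraction r, a 20% rise over the 1 h gas is a rise of 1.2(1 + r) − 1 over the earlier gas. For r = +5%, +10%, +20% this is 26%, 32%, 44%. For r = −5%, −10%, −20% it is 14%, 8%, −4%. This is only a conversion; it does not say which reference is right.

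**4. Simulation.** 200,000 patients were simulated with normal values, a between-patient SD of 3 mmHg and a within-patient SD of 2, 3 or 4 mmHg. An event is any later gas at least 1.2 times the reference. Entries are for within-patient SD 2 / 3 / 4.

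| Assumed mean profile (pre-op; 1, 6, 12, 24 h) | Events of 20, pre-op reference | Events of 20, 1 h reference | Patients classified differently |
|---|---|---|---|
| 40; 40, 40, 40, 40 | 0.4 / 2.4 / 4.9 | 0.3 / 2.0 / 4.2 | 3% / 18% / 31% |
| 38; 43, 42, 41, 40 | 5.7 / 8.5 / 10.3 | 0.0 / 0.7 / 2.1 | 28% / 42% / 49% |

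With a flat profile the totals are close, although the patients counted can differ. A large gap in totals needs CO₂ to shift between the candidate times.

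**5. ANCOVA for POD3 FEV1/FVC.** Assume N = 20 analysed, 10 per arm, and a pre-op to POD3 correlation ρ. The variance ratio, adjusted to unadjusted, is (1 − ρ²)(N − 3)/(N − 4) = (1 − ρ²) × 17/16.

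- ρ = 0.3: 0.91 × 1.0625 = 0.967, a cut of about 3%.
- ρ = 0.5: 0.75 × 1.0625 = 0.797, a cut of about 20%.
- ρ = 0.7: 0.51 × 1.0625 = 0.542, a cut of about 46%.
- Break-even: ρ = √(1 − 16/17) = 0.243.

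In simulated trials the adjusted 95% CI was wider than the unadjusted one in about 52%, 20% and 3% of trials at these three correlations.

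**6. Effect of the FEV1 exclusion.** Patients below 75% predicted are excluded, which narrows the pre-op range. Assume FEV1 % predicted is normal with mean 85, 90 or 95 and SD 15 before exclusion. The share of pre-op variance kept is k = 0.53, 0.63 or 0.73. The correlation becomes ρ√k / √(ρ²k + 1 − ρ²). At means 85 to 95, ρ = 0.3 falls to 0.22–0.26, 0.5 to 0.39–0.44 and 0.7 to 0.58–0.64. The variance ratios are then 1.01 to 0.99, 0.90 to 0.85 and 0.70 to 0.63. The cuts are therefore about −1 to 1%, 10 to 15% and 30 to 37%.

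**The case against.** The strongest reply is that this is a small pilot in which significance is explicitly not the focus. Four of the five events are unaffected, no stopping rule uses event 2, and CO₂ at the four times is a secondary endpoint, so the raw values remain. For spirometry, both values are collected and adjustment stays possible later. At a correlation of 0.3 it gains almost nothing and often widens the interval. All of this stands, and it is why the point is minor. It does not supply the missing reference.

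A reader might infer more than the documents support:

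- **That a pre-device gas is the true reference, so a 1 h reference misses or over-counts events.** No section names a correct reference. The results show only that the choices disagree. A gas drawn under ventilation has its own weakness, because a later rise may reflect leaving the ventilator.
- **That the protocol expects CO₂ to fall.** General Design Limitations mentions "evidence of hyperventilation and/or respiratory alkalosis" only in connection with subjects opting out. It does not predict the direction of any difference.
- **That event 2 counts or FEV1/FVC estimates will size the next trial.** The Statistical Analysis Plan section names variability and effect sizes for PaO₂ only.
- **That the printed CO is a substantive error.** It may be a lost subscript, since CO₂ and PCO₂ appear elsewhere. Nothing here rests on it.

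**Conclusion.** The point holds, as a minor one. Event 2 cannot be applied with the planned data under the protocol's only meaning of Baseline, and its count depends on which gas is taken instead. That dependence follows from the text. Its size and direction do not: they rest on assumed CO₂ values, and range from a small difference in totals under a flat profile to about 8.5 against 0.7 patients of 20 under an assumed 38-to-43 mmHg shift (within-patient SD 3).

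The FEV1/FVC point is a cheap improvement rather than a flaw. Randomization already keeps the unadjusted comparison unbiased, so the gain is precision for this secondary endpoint only. It ranges from about none to about 46%, depending on a correlation the documents do not give and on how far the FEV1 exclusion narrows the pre-op range. These figures do not carry over to PaO₂ or the film score.

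**What to change.** **Event 2.** Before outcome data are reviewed, the sponsor and investigator should reconcile item 2 with the Schedule by designating one reference measurement: one time point and one ventilation/oxygen condition, the same in both arms.

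- Add no draw. If a chart gas is chosen, the protocol already provides a route: "Study data will be collected from the patient's electronic medical records". The documents do not show that a suitable gas exists for every patient, so report those without it as not assessable and give their number.
- Show raw CO₂ at the four times, by arm, beside the event count.
- State the limitation of whichever reference is chosen: leaving the ventilator if it is a ventilated gas, prior requested device use if it is the 1 h gas. Appendix A also asks both arms to practise before surgery, so a post-operative reference is not free of all device exposure.

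**Spirometry.** Compare POD3 FEV1 and FVC between arms by ANCOVA on the pre-op value, reported beside the unadjusted summary.

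**Cost.** Wording changes and, if a chart gas is designated, abstraction of one recorded value per patient. ANCOVA uses one degree of freedom and gives a wider interval in about half of trials if the correlation is only 0.3.

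As a small wording point, the Schedule marks a chest film with severity score under Baseline, whereas the endpoint and procedure text begin immediately after surgery. The two should be made to agree.
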